7.2.3 Exclusion criteria related to the current knowledge of alirocumab

- E 26. Hypersensitivity to alirocumab or to any of the ingredients of alirocumab injections.
- E 27. Females who have experienced menarche who are unwilling or unable to be tested for pregnancy.

Note: Females who have experienced menarche must have a confirmed negative pregnancy test at screening and other study visits. Pregnancy tests may be performed more frequently in some countries due to local legislations related to women of childbearing potential randomized in clinical trials.

- E 28. Positive pregnancy test in females who have experienced menarche.
- E 29. Females who are breast-feeding.
- E 30. Females of childbearing potential not protected by highly-effective method(s) of birth control (see contraceptive guidance in Appendix D).

Note: Females of childbearing potential must use an effective contraceptive method throughout the entire duration of the study treatment and for at least 10 weeks after the last injection.

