Appendix D Guidance on contraceptive methods and collection of pregnancy information

Reproductive potential (WOCBP)

A woman is considered of reproductive potential (WOCBP), ie, fertile, following menarche and until becoming postmenopausal unless permanently sterile. Permanent sterilization methods include hysterectomy, bilateral salpingectomy and bilateral oophorectomy.

CONTRACEPTIVE GUIDANCE

Sexual counseling should be provided to patients when indicated.

Female subjects:

Highly Effective Contraceptive Methods That Are User Dependent

*Failure rate of <1% per year when used consistently and correctly*⁶

- Combined (estrogen- and progestogen-containing) hormonal contraception associated with inhibition of ovulation:
 - Oral,
 - Intravaginal,
 - Transdermal.
- Progestogen-only hormone contraception associated with inhibition of ovulation:
 - Oral,
 - Injectable.

Highly Effective Methods That Are User Independent

- Implantable progestogen-only hormone contraception associated with inhibition of ovulation.
- Intrauterine device (IUD).
- Intrauterine hormone-releasing system (IUS).

Sexual abstinence

Sexual abstinence is considered a highly effective method only if defined as refraining from heterosexual intercourse during the entire period of risk associated with the study drug. The reliability of sexual abstinence needs to be evaluated in relation to the duration of the study and the preferred and usual lifestyle of the subject.

⁶ Typical use failure rates may differ from those when used consistently and correctly. Use should be consistent with local regulations regarding the use of contraceptive methods for subjects participating in clinical studies.

COLLECTION OF PREGNANCY INFORMATION

Female subjects who become pregnant

- The Investigator will collect pregnancy information on any female subject, who becomes pregnant while participating in this study.
- Information will be recorded on the appropriate form and submitted to the Sponsor within 24 hours of learning of a participant's pregnancy.
- Participant will be followed to determine the outcome of the pregnancy. The Investigator will collect follow-up information on participant and neonate, which will be forwarded to the Sponsor. Generally, follow-up will not be required for longer than 6 to 8 weeks beyond the estimated delivery date.
- Any termination of pregnancy will be reported, regardless of fetal status (presence or absence of anomalies) or indication for procedure.

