
The incidence of liver related TEAEs will be summarized. The selection of PTs will be based on SMQ Hepatic disorder (see Section 2.1.4.1).

Gonadal hormones and pituitary hormones

Girls and boys will be described separately.

• For girls

The following analyses will be provided only in post-menarchal girls for at least 1 year at baseline and without receiving any oral contraceptive throughout the study.

- Changes from baseline will be tabulated by time point for estradiol and pituitary hormones (FSH and LH) during treatment period.
- Similar table as for PCSA will be provided using normal range during the TEAE period. The number (%) of patients with at least one estradiol value <LLN and LH >ULN, estradiol value<LLN and FSH >ULN, estradiol value <LLN and LH>ULN and FSH >ULN) during the TEAE period will be presented.

In addition, a listing of estradiol, LH, FSH values over time along with the tanner stage and date of last menses (if any) will be displayed for all girls.

• For boys

The following analyses will be provided only in boys with at least a Tanner stage 2

- Changes from baseline will be tabulated by time point for testosterone and pituitary hormones (FSH and LH) during treatment period.
- Similar table as for PCSA will be provided using the normal range. The number (%) of patients with at least one testosterone value <LLN and LH >ULN, testosterone

value<LLN and FSH >ULN, testosterone value<LLN and LH>ULN and FSH >ULN) during the TEAE period will be presented.

In addition, a listing of testosterone, LH, FSH values over time along with the tanner stage will be displayed for all boys.

Adrenal gland hormones

DHEAS:

Girls and boys will be described separately.

- Changes from baseline will be tabulated by time point.
- Similar table as for PCSA will be provided using the normal range during the TEAE period.

These summaries will be provided in post-menarchal girls for at least 1 year at baseline and without receiving any oral contraceptive throughout the study, and in boys with at least a tanner stage 2.

In addition, a listing of all values over time along with normal range will be provided.

Cortisol and ACTH

Girls and boys will be analyzed together. Samples not drawn between \geq 6:00 AM and <11:00 AM will be excluded.

- Changes from baseline will be tabulated by time point for cortisol during treatment period.

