- Similar table as for PCSA will be provided using the normal range during the TEAE period. The number (%) of patients with at least one cortisol <LLN, cortisol <LLN and ACTH >ULN will be presented.

Although the summaries for gonadal and pituitary hormones and DHEA will be provided as planned for safety endpoints (ie, by treatment groups within each dosing regimen cohort, and by treatment groups regardless of the dosing regimen cohorts), the analyses by treatment regardless of the dosing regimen cohorts (ie, pooled across the cohorts) appears the most relevant, due to the restriction of the population involved in those analyses (post-menarchal girls for at least 1 year at baseline and without receiving any oral contraceptive throughout the study, and in boys with at least a tanner stage 2).

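### The girls' hormone summaries drop oral contraceptive users only, although the protocol accepts four non-oral hormonal routes that it also describes as inhibiting ovulation

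*SAP*

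**What the plan says.** SAP section 2.4.5.3 sets the girls' analysis set in three places. Under gonadal and pituitary hormones, the analyses are provided "only in post-menarchal girls for at least 1 year at baseline and without receiving any oral contraceptive throughout the study". Under DHEAS: "These summaries will be provided in post-menarchal girls for at least 1 year at baseline and without receiving any oral contraceptive throughout the study". The closing paragraph, which prefers the analysis pooled over the Q2W and Q4W cohorts, cites the restricted population again: "post-menarchal girls for at least 1 year at baseline and without receiving any oral contraceptive throughout the study". None of the three mentions a route other than oral, and none gives a reason for the restriction.

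Protocol Appendix D lists the accepted highly effective methods. One group is "Combined (estrogen- and progestogen-containing) hormonal contraception associated with inhibition of ovulation", by the oral, intravaginal or transdermal route. A second is "Progestogen-only hormone contraception associated with inhibition of ovulation", oral or injectable. A third entry is "Implantable progestogen-only hormone contraception associated with inhibition of ovulation". The hormone-releasing intrauterine system is also accepted, but without any mention of ovulation. Abstinence can qualify under stated conditions.

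Exclusion criterion E 30 (protocol section 7.2.3) bars "Females of childbearing potential not protected by highly-effective method(s) of birth control". Appendix D counts a female as of reproductive potential from menarche.

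**The concern.** The evident purpose of the oral contraceptive restriction is to keep girls whose sex and pituitary hormones reflect contraception out of tables meant to show an effect of alirocumab. If so, the criterion should follow the mechanism and not the route. The protocol gives the ring, patch, injection and implant the same mechanism as the pill, yet a girl using one of these remains in the summaries.

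At stake is the readability of a paediatric safety check in a subset that the SAP itself regards as so restricted that the pooled analysis is the most relevant one. In a small set, one or two girls can move a mean change or a percentage outside the normal range. Starting such a method after baseline would appear as a change on treatment.

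**Working it through.** There is no plan figure to reproduce, so the check sets the two documents side by side and then asks in which direction each table could move.

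**1. Routes accepted against routes removed**

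| Method | Accepted in Appendix D | Described there as ovulation-inhibiting | Removed by SAP 2.4.5.3 |
|---|---|---|---|
| Oral (combined or progestogen-only) | yes | yes | yes |
| Intravaginal (combined) | yes | yes | no |
| Transdermal (combined) | yes | yes | no |
| Injectable (progestogen-only) | yes | yes | no |
| Implant (progestogen-only) | yes | yes | no |
| Hormone-releasing intrauterine system | yes | no | no |

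**2. Is the analysed set reached by the contraception rules?** Yes. The set consists of girls at least a year past menarche, and both E 30 and the Appendix D definition apply from menarche onward.

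**3. Does another rule remove non-oral users?** No. Protocol section 8.8.3 prohibits oral and injectable corticosteroids, fibrates other than fenofibrate, and immunosuppressants. The restriction on newly started estrogen in Appendix E binds FMD sub-study participants only.

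**4. Direction of effect, assuming suppressed hormones in a user**
- Change from baseline: moves if the method is started or stopped after baseline. It need not move if the method was already in use at baseline.
- Single-hormone normal-range table: can gain a girl below the lower limit of normal.
- Composite rows (low estradiol with LH and/or FSH above the upper limit): a girl with suppressed LH and FSH is unlikely to qualify but stays in the denominator, so these rows are diluted and not inflated.

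**5. Size.** The documents give neither the number of eligible girls nor the use of each method. The following is illustration only.
- Assume 30 to 50 eligible girls and 3% to 10% non-oral use: 30 × 0.03 = 0.9 and 50 × 0.10 = 5, so about 1 to 5 girls. Zero is equally compatible with the documents.
- One girl who does fall below the estradiol limit adds 1/50 = 2.0 to 1/30 = 3.3 percentage points to a percentage over all girls, or 1/40 = 2.5 with 40 girls.
- The tables are by treatment group. If 40 girls split 2:1, about 27 and 13, one such girl is 1/27 = 3.7 points on alirocumab or 1/13 = 7.7 points on placebo.
- Dilution of a composite row: one qualifying girl among 40 is 2.5%. With five users removed it is 1/35 = 2.9%.

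**The case against.** The strongest reply is that the wording gap is real but may have no consequence. Abstinence is an accepted method, and protocol sections 10.2 and 10.3.3 tie contraception records and the related stopping criterion to sexually active females, so there may be no non-oral users at all. The safety summaries are descriptive with no formal testing (SAP 2.4.5). In the double-blind period there is a concurrent randomised placebo group, and a method can be started in either arm. By-visit laboratory tables are not planned for the open-label period unless the data call for them. Normal-range tables may be split by baseline status, all girls appear in the estradiol, LH and FSH listing with Tanner stage and last menses, and concomitant medications are summarised, so an outlier can be traced. Pubertal development is also followed through Tanner stage (SAP 2.4.5.6).

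All of this stands, and it limits the consequence. It does not explain why one route is excluded and four with the same description are kept.

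A reader might infer more than the documents support:
- That contraceptive effects will be mistaken for drug effects. This needs users, an imbalance between arms or a start after baseline, and a reader who ignores the listing. None of these is established.
- That every non-oral user adds a fixed number of points. This assumes that each one falls below the estradiol limit, which no passage says.
- That the composite rows are inflated. Under the suppression premise they are diluted.
- That these methods alter DHEAS. The documents only show the SAP reusing the same restriction for it.

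**Conclusion.** The point holds as a mismatch between a stated analysis rule and its evident purpose. Followed literally, SAP 2.4.5.3 keeps users of four non-oral hormonal routes in the girls' estradiol, LH, FSH and DHEAS summaries while removing users of oral products that the protocol describes in the same terms. The girls' set is also limited by time since menarche, so oral use is the only contraceptive ground for exclusion but not the only restriction.

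The number affected is unknown and may be zero. If there are users, single-hormone and change-from-baseline summaries can shift by a few points per girl within an arm, and composite rows are slightly diluted. No efficacy result or tested hypothesis is involved.

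The conclusion rests on two inferences: that the restriction is meant to remove contraceptive influence on these hormones, and that inhibition of ovulation implies altered estradiol, LH and FSH. For DHEAS the case is weaker and rests on consistency with the SAP's own rule.

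**What to change.** In all three places in SAP 2.4.5.3, replace the oral contraceptive condition with: any ovulation-inhibiting hormonal contraceptive, whatever the route (oral, intravaginal, transdermal, injectable or implant). Identify users from the medication pages, which already cover 12 weeks before screening to the end of study and are coded with WHO-DD (SAP 2.1.2). Check that long-acting products placed earlier were recorded as ongoing. State separately whether users of the hormone-releasing intrauterine system are kept or excluded, because the ovulation rationale does not settle it.

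The cost is one phrase, one medication-code list and a decision on the intrauterine system. A few girls may leave an already small summary set, though all girls stay in the estradiol, LH and FSH listing. The exclusion would still depend partly on use after randomisation, as it does now, since the condition runs over the whole study. The SAP should acknowledge this and report the number excluded by treatment group.

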2.4.5.4 Analyses of vital sign variables

The summary statistics (including number, mean, median, standard deviation, minimum and maximum) of all vital signs variables (heart rate, diastolic and systolic blood pressure in sitting position), height, height percentile, weight, BMI and BMI percentile (value and change from baseline) will be calculated for each visit or study assessment (baseline, each post-baseline value of the treatment period, last on-treatment, worst on-treatment value). For weight, percent change

from baseline will also be presented. In addition, summaries by gender will be provided for height, weight and BMI. Heart rate and blood pressure without position filled in will only be used for the PCSA analysis described below.

The incidence of PCSAs for heart rate and blood pressure at any time during the TEAE period will be summarized.

For OL vital signs parameters, summary tables as described for the double-blind period above will be used with the following exceptions:

• Analyses by visit (unless data warrants further investigation)

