1.3 DETERMINATION OF SAMPLE SIZE

Each alirocumab dosing regimen group will be compared to its contemporaneously randomized placebo group (ie, of the same dosing regimen cohort) as follows:

- alirocumab Q2W versus placebo Q2W
- alirocumab Q4W versus placebo Q4W

Of note, Q2W and Q4W refer to the dosing regimens initiated at randomization.

Multiplicity will be controlled using Bonferroni adjustment, hence using a two-sided alpha level of 0.025 for each comparison.

With a randomization ratio of 2:1 (alirocumab: placebo) for each dosing regimen cohort, a total sample size of 90 patients (30 in each alirocumab dosing regimen group and 15 in each placebo dosing regimen group) will have 92% power to detect a difference in mean percent change in LDL-C of 30% in any comparison between each alirocumab dosing regimen group and its contemporaneously randomized placebo dosing regimen group with a 0.025 two-sided significance level and assuming a common standard deviation (SD) of 25%.

Nevertheless, to have a sufficient number of pediatric patients for properly assessing the safety and tolerability of alirocumab, sample size was increased to 150 patients in total (50 in each alirocumab dosing regimen group and 25 in each of the placebo dosing regimen group). The enrollment of 150 patients will allow for a safety assessment over 2 years in approximately 128 patients, assuming a discontinuation rate of 15%.

Calculations were made using nQuery 7.0 Advisor software.

Sample Size Determination for the FMD sub-study:

Assuming that 30 to 39 patients (regardless of the dosing regimen cohort: 20 to 26 in the alirocumab group and 10 to 13 in the placebo group) will participate in the sub-study, the statistical power to demonstrate superiority of alirocumab versus placebo at a 0.05 two-sided significance level is provided in Table 1. This sample size calculation is based on several assumptions for the mean difference and standard deviation (SD) of the absolute change from baseline to Week 24 in flow mediated dilatation of the brachial artery that are enumerated in Table 1.

Expected number	Standard	Delta mean (%)		
of patients (2:1 ratio)	deviation [—] (%)	2	2.5	3
30	2.5	51%	70%	84%
	4	23%	34%	46%
39	2.5	63%	81%	93%
	4	29%	43%	57%

Table 1 - Statistical power according to mean difference and SD of the FMD absolute change from baseline to Week 24

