2 STATISTICAL AND ANALYTICAL PROCEDURES

2.1 ANALYSIS ENDPOINTS

2.1.1 Demographic and baseline characteristics

The baseline value is defined as the last available value obtained before or equal to the date and time of the first double-blind Investigational Medicinal Product (IMP) injection in the EFC14643 study. In case of missing time of the first double-blind IMP injection and/or time of assessment, the baseline value is defined as the last available value obtained before or equal to the date of the first double-blind IMP injection.

For patients randomized and not treated, the baseline value is defined as the last available value obtained before or equal to the date and time of randomization. In case of missing time of assessment, the baseline value is defined as the last available value obtained before or equal to the date of the randomization.

All baseline safety and efficacy parameters are presented along with the summary statistics in the safety and efficacy sections (Section 2.4.4 and Section 2.4.5).

Demographic characteristics

Demographic variables include:

- Gender (Male, Female).
- Age in years (quantitative and categorical variable: <12 and ≥ 12 to <18 years, as well as $<10, \ge 10$ to <12, and ≥ 12 to <18 years).
- Race (White, Black or African American, Asian, American Indian or Alaska Native, Native Hawaiian or other Pacific Island, other).
- Ethnicity (Hispanic or Latino, Not Hispanic or Latino).
- Weight in kilograms (quantitative and categorical variable: <50 and ≥ 50 kg).
- Height in centimeters (quantitative variable).
- Body mass index (BMI) in kg/m² (quantitative and categorical variable: <P5: Underweight, ≥P5 to <P85: Healthy weight, ≥P85 to <P95: Overweight and ≥P95: Obesity, using the World Health Organization [WHO] growth reference 5-19 years (1, 2, 3).

Medical or surgical history

Medical or surgical history includes medical history of specific interest such as cardiovascular (CV) history and cardiovascular risk factors, subject medical allergic history and family medical allergic history, and relevant medical or surgical history other than hypercholesterolemia, CV/CV

Risk and allergies. Medical and surgical history will be described using all pre-printed terms collected in the dedicated medical history e-CRF pages.

CV history and CV Risk factors history will be based on items pre-listed in the dedicated medical history e-CRF page and include:

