2.1.4.4 Vital signs variables

Vital Signs parameters include Heart Rate (HR), Systolic and Diastolic Blood Pressure (SBP and DBP) in sitting position, as well as weight, height and BMI.

Body weight was to be measured during:

- Run-in (if applicable) at Visit 1 (up to Week -6) or Screening at Visit 2 (up to Week -2).
- The double-blind period at Visit 4 (Week 0/Day 1), Visit 6 (Week 12), Visit 7 (Week 24)/or early termination.

• The OL period at Visit 8 (Week 32), Visit 9 (Week 44), Visit 11 (Week 68), Visit 13 (Week 92) and Visit 14 (Week 104)/or early termination for patients proceeding into OL period.

Height was to be measured during:

- Run-in (if applicable) at Visit 1 (up to Week -6) or Screening at Visit 2 (up to Week -2).
- The double-blind period at Visit 7 (Week 24)/or early termination.
- The OL period at Visit 9 (Week 44), Visit 11 (Week 68) and Visit 14 (Week 104)/or early termination for patients proceeding into OL period.

BMI and height percentiles will be calculated (1, 2, 3).

Heart rate and blood pressure were to be measured during:

- Screening at Visit 2 (up to Week -2).
- The double-blind period at Visit 4 (Week 0/Day 1), Visit 6 (Week 12), Visit 7 (Week 24) /or early termination.
- The OL period at Visit 8 (Week 32), Visit 9 (Week 44), Visit 11 (Week 68) and Visit 14 (Week 104)/or early termination for patients proceeding into OL period.

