2.4 STATISTICAL METHODS

General rules

Analyses will be performed separately for the double-blind and the OL periods, unless otherwise noted.

Double-blind period

Unless otherwise specified, the analyses will be performed by treatment group (placebo, alirocumab) within each dosing regimen cohort.

In addition, for disposition, populations, demographic/baseline characteristics, safety and other endpoints (refer to Section 2.1.5), analyses will be provided by treatment group (placebo, alirocumab) regardless of the dosing regimen cohorts (pooled across cohorts).

Of note, an Overall column will be displayed for populations, demographics and baseline characteristics.

OL period

The summaries will be displayed according to the treatment group (placebo, alirocumab) received in the double-blind period and Overall within each dosing regimen cohort (dosing regimen initiated at the randomization).

For disposition, populations, demographic/baseline characteristics, safety and other endpoints, analyses will be also provided by treatment group received in the double-blind period regardless of the dosing regimen cohorts, and Overall.

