2.4.5 Analyses of safety data

No formal inferential testing will be performed for either study period. Summaries will be descriptive in nature. All summaries of safety results described below will be presented for each study period respectively, unless otherwise noted.

General common rules

All safety analyses will be performed on the safety population for the double-blind period and on the OL population for the OL period, as defined in Section 2.3.2 unless otherwise specified, using the following common rules:

- Safety data in patients who do not belong to the safety population (ie, exposed but not randomized) will be listed separately.
- The baseline value for both double-blind and OL periods is defined as the last available value obtained up to the date and time of the first double-blind IMP injection in EFC14643 study, except otherwise specified.
- PCSA values are defined as abnormal values considered medically important by the Sponsor according to predefined criteria/thresholds based on literature review and defined by the Sponsor for clinical laboratory tests and vital signs, PCSA in children [Appendix A] and PCSA in adults version dated May 2014 [Appendix B]). Considering that the threshold defined in the PCSA list for monocytes and basophils can be below the ULN, the following PCSA criteria will be used for the PCSA analysis of monocytes and basophils:
 - PCSA criterion for monocytes: >0.7 Giga/L or > ULN (if ULN ≥ 0.7 Giga/L)
 - PCSA criterion for basophils: >0.1 Giga/L or > ULN (if ULN \ge 0.1 Giga/L)
- PCSA criteria will determine which patients had at least 1 PCSA during the TEAE period, taking into account all evaluations performed during the TEAE period, including nonscheduled or repeated evaluations.
- The treatment-emergent PCSA denominator by group for a given parameter will be based on the number of patients assessed for that given parameter at least once during the TEAE period.
- All measurements, scheduled or unscheduled, fasting or not fasting, will be assigned to analysis windows defined in Section 2.5.4, Table 5 and Table 6 in order to provide an assessment for Week 4 to Week 104 time points.

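### Percentiles are the only age-adjusted growth summaries, and change in percentile is compressed in the tails; change in height and BMI z-score should be added

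*SAP*

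**What the plan says.** SAP 2.1.4.4 defines the derived growth measures: "BMI and height percentiles will be calculated (1, 2, 3"). SAP 2.4.5.4 then states that "height, height percentile, weight, BMI and BMI percentile (value and change from baseline) will be calculated for each visit or study assessment", using "The summary statistics (including number, mean, median, standard deviation, minimum and maximum) of all vital signs variables". It adds percent change for weight, and summaries by gender for height, weight and BMI. For the open-label period the by-visit tables are dropped unless the data call for them.

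SAP 2.1.1 classifies baseline BMI "using the World Health Organization [WHO] growth reference 5-19 years" and cites the same three references as 2.1.4.4, so I read the reference as common to both sections.

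SAP 2.4.5 says of safety data: "No formal inferential testing will be performed for either study period. Summaries will be descriptive in nature". SAP 2.4 adds that for safety "analyses will be provided by treatment group (placebo, alirocumab) regardless of the dosing regimen cohorts (pooled across cohorts"). With 50 and 25 patients per cohort (SAP 1.3), that is about 100 against 50.

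Neither document mentions a z-score for height or BMI. The SAP does use age-matched z-scores for the Cogstate tests (2.1.4.7 and Appendix E).

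**The concern.** Height and body weight are listed safety parameters in Protocol 9.2.4, in patients aged 8 to 17 followed for up to 104 weeks of treatment. Children of that age grow anyway, so change has to be read against an age reference. The plan provides one, but on a scale that shrinks towards zero at both ends. Averaging changes on it gives children near the median most of the weight and children in the tails very little. The z-score from which the percentile is obtained does not have this defect.

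At stake is how clearly the growth tables would show a modest slowing, above all in the shortest children.

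**Working it through.** **Inputs from the documents.** Summaries as quoted above; 150 patients in all, 2:1; no formal safety test. The documents give no effect size, SD, alpha or power for growth, so there is no growth figure to reproduce. The plan's only main-study power figure is for LDL-C: "92% power to detect a difference in mean percent change in LDL-C of 30"%, with 30 against 15 patients, SD 25 and two-sided alpha 0.025. The standard error is 25 × √(1/30 + 1/15) = 7.906 and the noncentrality is 30/7.906 = 3.795. The noncentral t with 43 df gives 92.5%, so that figure reproduces. It has no bearing on growth.

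**Step 1: compression.** Percentile P = 100 × Φ(z). For a loss of 0.5 SD:
- from the median (z = 0): 50 − 100 × Φ(−0.5) = 50 − 30.85 = 19.1 points;
- from the 3rd percentile (z = −1.881): 3 − 100 × Φ(−2.381) = 3 − 0.86 = 2.1 points;
- from the 1st percentile (z = −2.326): 1 − 100 × Φ(−2.826) = 1 − 0.24 = 0.8 points.

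A smaller loss behaves the same way: 0.25 SD is 9.9 points at the median and 1.05 at z = −2, about one ninth. This follows from the scale alone and needs no trial assumption.

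**Step 2: precision.** For small changes, ΔP ≈ 100 × φ(z₀) × Δz. Assume the treatment effect on z is the same for every child, Δz is independent of baseline z₀, and the mean change is small relative to its SD. The efficiency of mean ΔP relative to mean Δz is then

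RE = (E[φ(z₀)])² / E[φ(z₀)²].

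For z₀ ~ N(m, s²) this equals √(1+2s²)/(1+s²) × exp{−m²/(1+s²) + m²/(1+2s²)}. With m = 0 and s = 1 it is √3/2 = 0.866.

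| Assumed baseline z | RE | 150 × RE |
|---|---|---|
| mean 0, SD 0.8 | 0.921 | 138 |
| mean 0, SD 1 | 0.866 | 130 |
| mean ±0.5, SD 1 | 0.831 | 125 |
| mean ±1, SD 1 | 0.733 | 110 |
| mean ±1, SD 1.2 | 0.693 | 104 |

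The last column is the number of patients who would give the same precision on the z scale. If baseline BMI is cut off at the 95th percentile, RE is about 0.86 to 0.93 for means 0 to 1 and SDs 0.8 to 1.2. A mean as far out as 1.5 with SD 1 would give 0.595. All these baselines are assumptions.

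**The case against.** A reader might infer that the plan loses some 6 to 15 points of power. The documents do not support that: no growth comparison is tested. The figure appears only if one invents a two-sided 0.05 test in which the z-score has 80% power. The percentile power is then Φ(2.80 × √RE − 1.96), a loss of 5.9 points at mean 0, SD 1 and 15.5 at mean ±1, SD 1.2. Other baselines give 3.3 points (mean 0, SD 0.8) to 22.0 (mean 1.5, SD 1), and about 4 to 5 for most baselines with BMI cut at the 95th percentile. The treated-against-control contrast behind such a figure also exists only for the 24 double-blind weeks.

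A reader might also infer that growth loss would be hidden. It would not be hidden everywhere. Median, minimum and maximum are reported beside the mean; raw height, weight and BMI are tabulated; Tanner stage is summarised separately. In the randomised period, raw height change against concurrent placebo is a fair comparison, because age is balanced in expectation.

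Further points against are that growth is not among the risks in Protocol section 4 or the events of special interest in 10.4.1.3, and that the number of very short children is unknown. Exclusions E03 (weight below 25 kg) and E04 (Tanner stage) may remove some of them, and E09 may trim the upper BMI tail.

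All of this limits the size of the point. It does not repair the scale. The median, minimum and maximum of percentile change are still on the compressed scale, and the largest changes tend to come from mid-range children. After Week 24 every patient receives alirocumab and, as SAP 2.4.4 notes, there is no control group, so raw height gain cannot be interpreted without age adjustment. There is no categorical backstop for height either: the abnormality lists in SAP Appendices A and B contain no height criterion.

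**Conclusion.** The point stands as a minor improvement to descriptive safety tables. The only age-adjusted growth summaries use a scale on which a given loss near z = −2 shows at about one ninth of its size at the median. Under a uniform shift in z, their efficiency is about 0.87 of the z-score's for a standard normal baseline, and about 0.69 to 0.93 over baseline means 0 to ±1 and SDs 0.8 to 1.2, with or without the BMI cut-off. The compression is certain. The efficiency depends on a baseline distribution that the documents do not give. What is lost is precision and ease of interpretation, chiefly for very short children and for the open-label period. No planned power, type I error or efficacy conclusion is affected.

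**What to change.** In SAP 2.1.4.4, derive height-for-age and BMI-for-age z-scores from the WHO reference already used for the percentiles. In 2.4.5.4, summarise their value and change from baseline, and name them the main age-adjusted growth summary for both the double-blind and open-label periods. Percentiles need not be deleted: they can stay as a secondary display and for the baseline BMI categories.

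The cost is SAP wording and one extra derived variable per measure, with no new data or visits. The downside is units slightly less familiar to some readers.
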